PACU clinicians are responsible for several clinical and organizational tasks⁵ including patient monitoring and treatment, promoting patient throughput, conducting hand-offs to and from the PACU, and documenting patient care information during the recovery period. As a result, PACU nurses and doctors can feel overwhelmed, and may not always be able to treat symptoms adequately, diagnose physiological derangements accurately, and detect patient deterioration expeditiously. Furthermore, in this high-pressure, high-turnover environment, communication among clinicians is often compromised, resulting in unreliable care coordination. Patient

satisfaction with PACU care varies, as the recognition and prompt treatment of symptoms depends on the availability of assigned clinicians.

The necessity of operating room throughput creates a constant pressure on PACU clinicians to discharge patients rapidly, sometimes before they have recovered sufficiently. This workflow pressure can potentially compromise quality of care and patient safety. Nurses provide the majority of PACU care, typically for no more than two patients at a time during the initial phase of PACU care, in accordance with the American Society of PeriAnesthesia Nurses (ASPN) guidelines⁶. Furthermore, physicians with competing responsibilities often provide oversight in the PACU. For example, a physician who has responsibility for patient assessment and management in the PACU is often simultaneously overseeing anesthetic care in operating rooms or other procedural suites. Surgical clinicians also participate in aspects of PACU care, but are often simultaneously engaged in surgical care of other patients. In addition, the coverage and oversight models can vary considerably across different PACUs, and even within the same PACU over the course of a single day. This is in stark contrast to other high acuity patient care settings, such as operating rooms and intensive care units, where roles and responsibilities of various clinicians are well defined, and staffing models are established.

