Severe pain (Numerical Rating Scale >7/10)	Itching
Chest pain unrelated to surgery	

Table 4. Emergency medical interventions

Did the telemedicine center contact PACU clinicians for any of the following interventions:	
Intubation	Unplanned transfusion
Assisted ventilation	Naloxone administration
Cardiopulmonary resuscitation	Return to OR
Cardioversion	Other (free text box)
If Yes, please check all that apply:	
 PACU nurse already aware of the situation	
 PACU nurse unaware of the situation	
 PACU nurse disagreed with the assessment	
 PACU nurse had already spoken to the supervising physician regarding the situation	

Other (please describe):

*Only the telemedicine center will document the detection of urgent situations.

Table 5. Patient discharge readiness

At what time did the patient sufficiently recover to be discharged (case attending anesthesiologist contacted for discharge)?	
PACU Nurses	Telemedicine Center for PACU
Time anesthesiologist is contacted for discharge evaluation	Time ready for discharge
Aldrete Score at discharge	Aldrete Score at discharge
	Unable to determine patient's readiness for discharge
Modified Aldrete Scale Component and Scoring Parameters	If Unable to fully assess, select reason(s) why (Checkbox)
Respiration	 More patient information needed  Equipment issues  Patient cooperation  Other (free text box)
2 – Able to take deep breath and cough	
1 – Dyspnea / Shallow Breathing	
0 – Apnea	
O₂ Saturation	
2 – Maintains > 92% on room air	
1 – Needs O ₂ inhalation to maintain O ₂ saturation > 90%	
0 – Saturation <90% even with supplemental O ₂	
Consciousness	
2 – Fully awake	
1 – Arousable on calling	
0 – Not responding	
Circulation	
2 – BP ± 20mmHg pre-op	
1 – BP ± 20-50mmHg pre-op	
0 – BP ± greater than 50mmHg pre-op	
Motor Activity	
2 – Able to move 4 extremities voluntarily or on command	
1 – Able to move 2 extremities voluntarily or on command	
0 – Able to move 0 extremities voluntarily or on command	

Interaction Phase (3 months)

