This is a proof-of-concept study and will only address surrogate outcomes. The primary outcome (time to PACU discharge readiness) will use two comparison groups. First, historical controls will be drawn from the observation phase. A propensity score for inclusion into the study will be generated as a function of (minimally) surgery performed, day of week, time of day, age, and sex. 3:1 matched control patients will be included. The outcome will be analyzed with interrupted time series methods with flexible functions of calendar time used to adjust for secular trends; the study hypothesis is a non-zero discontinuity at telemedicine implementation.

That is, if Y_i is the outcome for the i th patient at time t_i with covariate vector X_i , while the implementation time is t_0 , and $I()$ is the indicator function,

$$Y_i = f_1(t_i)I(t_i < t_0) + f_2(t_i)I(t_i \geq t_0) + X_i\beta + \epsilon H_0: f_1(t_0) = f_2(t_0)$$

where f_1 and f_2 are smooth functions. Other patient factors known to strongly influence PACU length of stay (age, ASA physical status, number of co-morbidities, morbid obesity, obstructive sleep apnea, surgical specialty, primary anesthesia type, history of postoperative nausea and vomiting, preoperative pain, and scheduled case duration) will be included as covariates. The minimization criteria will be least squares or trimmed least squares or other robust criteria if there are substantial outliers. Outcomes will be examined for residual auto-correlation, and if non-negligible, auto-correlation robust standard errors (such as Newey-West errors) and an ARIMA model will be reported. Confidence intervals will be generated by non-parametric bootstrap sampling where possible. No adjustment will be made for matching, but bootstrap methods will respect the matched “units.” P-values will be generated both by likelihood ratio tests and by using non-deployment times as a null distribution; that is, we will run the same analysis looking for discontinuity at times remote from the true implementation time. We will conduct sensitivity analyses with transformations of the outcome variable. We will use an excluded run-in period of 1 month as a sensitivity analysis. Because hospital length of stay is unlikely to be meaningfully affected by a telemedicine center for the PACU, but does track overall acuity and surgical severity, we will use hospital length of stay as a control time series.

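### The historical-control interrupted time series has no measure of PACU workload, so a change in unit load at the phase switch would be absorbed into the estimated discontinuity, in either direction

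*Combined protocol and SAP*

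**What the plan says.** The Introduction describes the unit's working conditions. "The necessity of operating room throughput creates a constant pressure on PACU clinicians to discharge patients rapidly", and it adds that "the coverage and oversight models can vary considerably across different PACUs, and even within the same PACU over the course of a single day".

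Table 5 defines the nurse-side readiness time as "Time anesthesiologist is contacted for discharge evaluation". That is something a member of staff does, so it can respond to workload as well as to the patient's recovery.

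Under Statistical Methods, Primary Outcome, time to discharge readiness is analysed against two comparison groups.

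- **Historical controls.** These come from the observation phase, are matched 3:1, and are analysed by ITS. The null hypothesis is f1(t0) = f2(t0), where f1 and f2 are separate smooth functions of calendar time before and after implementation. The covariates in X_i are introduced as "Other patient factors known to strongly influence PACU length of stay" and listed as "age, ASA physical status, number of co-morbidities, morbid obesity, obstructive sleep apnea, surgical specialty, primary anesthesia type, history of postoperative nausea and vomiting", then "preoperative pain, and scheduled case duration) will be included as covariates".
- **Contemporaneous controls.** These are also matched 3:1, on a propensity score that includes calendar time and time of day. The comparison is a permutation-calibrated t-test. A sensitivity analysis pools both control groups in the ITS with one study-patient indicator T.

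The historical propensity score includes day of week and time of day. Both propensity lists are stated as minimum sets; the list for X_i is not. No census, staffing or operating-room volume variable appears in either score or in any outcome model.

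**The concern.** The ITS tests for a jump at t0. Smooth functions on each side can remove gradual drift, but they are free to differ at t0, so they cannot remove a step that happens there. If block schedules, staffing or a holiday period changed the load on the PACU at about the time the interaction phase began, the model would have no means of separating that change from telemedicine.

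The error could go either way. A busier unit might discharge sooner under throughput pressure, which would look like benefit. It might instead call the anesthesiologist later because staff are stretched, which would hide a benefit. The Introduction gives grounds for both: it describes pressure to move patients on, and it also describes overloaded staff and supervising physicians with competing duties.

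At stake is the interpretation of one of the two primary comparisons in a study powered for a 20-min difference. Variation in load that has nothing to do with the switch also adds noise, and same-day correlation, to the outcome.

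**Working it through.** **Inputs from the plan (Primary Outcome).** SD 65 min; 250 patients per phase; target decrease 20 min; bootstrap standard error (SE) 5.5 min with 3:1 controls.

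**Assumptions, not in the documents.** Two-sided alpha 0.05; a load step of b min exactly at t0; zero telemedicine effect; linear f1 and f2; patients spread evenly over time.

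**Step 1: the plan's own figures.** SE of a difference in means = 65 × √(2/250) = 5.81 min. Power = Φ(20/5.81 − z): 93.1% with z = 1.960 (alpha 0.05) and 73.7% with z = 2.807 (alpha 0.005). Both meet the stated bounds of more than 90% and more than 70%. The confidence interval width is 2 × 1.96 × 5.5 = 21.6 min, against a stated 22. These figures are not in dispute.

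**Step 2: SE of the ITS jump.** With a straight line fitted on each side and patients spread evenly, the variance of the fitted value at t0 is about 4σ²/n per side. The SE of the jump is then about 2 × 5.81 = 11.6 min for 500 patients.

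**Step 3: false-positive rate.** The step b passes one-for-one into f2(t0) − f1(t0). The rejection rate is Φ(b/SE − 1.96) + Φ(−b/SE − 1.96). The last three columns come from 2,000 simulated trials per row, in which a load variable carried the step.

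| Assumed step b (min) | ITS, formula | ITS, simulated (mean estimate) | ITS with load variable added | Contemporaneous controls sharing the load |
|---|---|---|---|---|
| 0 | 5.0% | 4.7% (0.0) | 4.9% | 5.0% |
| 5 | 7.1% | 7.3% (4.7) | 6.0% | 5.0% |
| 10 | 13.8% | 14.1% (9.9) | 5.1% | 4.8% |
| 15 | 25.2% | 25.8% (15.5) | 4.5% | 5.3% |
| 20 | 40.5% | 37.0% (19.5) | 5.0% | 4.8% |

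**Step 4: sensitivity to sample size.** Steps 2 and 3 use 500 patients. If the ITS instead set 250 study patients against 750 matched controls, the SE would be about 2 × 65 × √(1/250 + 1/750) = 9.5 min, and steps of 5 and 10 min would give about 8% and 18%. More flexible f1 and f2 would raise the SE and lower the rejection rate, but the bias would remain.

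**Step 5: do the plan's other devices remove the step?**

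- *Hospital length of stay as a control series.* It is chosen because it tracks acuity and surgical severity. A change in PACU load need not show in it.
- *Non-deployment dates as a null distribution.* If similar load steps occur at other dates, they widen the null distribution and the p-value becomes more honest. The estimate stays biased.
- *Day of week and time of day in the historical score.* These balance the regular weekly and daily pattern, not a change between phases.
- *Newey-West errors and ARIMA.* These deal with correlation, not bias.

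**Step 6: the contemporaneous comparison.** The last column shows it is unbiased when controls share the load change. The plan does not say that controls come from the same PACU. Study Size leaves bay allocation to the charge nurse's discretion, so load at arrival may differ between study and control patients even within one unit.

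**The case against.** The strongest reply is that the plan already has a second primary comparison built for this problem. Contemporaneous controls in the same PACU would live through the same change in load, and step 3 shows the bias then vanishes with no workload covariate. That stands. A reader might infer that the plan as a whole would read a load change as a telemedicine effect; the documents do not support this, and the point is confined to the historical ITS. What remains open is where the contemporaneous controls come from.

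Four further objections have force.

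- **Size.** A raw before-after difference in means would give 40.5% false positives for a 10-min step. A reader might quote that figure, but the plan specifies an ITS for this comparison, so the ITS column is the relevant one.
- **Staff availability.** A reader might cite the remark that "the recognition and prompt treatment of symptoms depends on the availability of assigned clinicians" as evidence that staffing drives discharge. It belongs to a sentence about patient satisfaction and symptom care, not discharge timing. The throughput statement carries the point, and it describes constant pressure, not pressure that differed between phases.
- **Sign and circularity.** The documents do not settle whether a higher census shortens or lengthens readiness time. The near-complete correction in the fourth column is partly built in, because the simulated confounder itself was added without measurement error. A real census would correct less.
- **Disclosure.** The limitations section concedes that improvements cannot be causally attributed and that confounding is possible. That is a fair general caveat, but it names no workload measure and does not replace adjusting for one that should be obtainable.

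The open-ended propensity lists would allow a workload variable to be added, but they do not pre-specify one and do not govern X_i.

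**Conclusion.** The concern holds for the historical-control ITS. Its covariates omit workload although the protocol itself names throughput pressure as a driver of discharge, and a load change at the switch would be absorbed into the discontinuity, in either direction. With an assumed step of 5 to 10 min and no telemedicine effect, the false-positive rate is about 7% to 14% in a linear-trend ITS with 500 patients, and the bias equals the step, or 25% to 50% of the 20-min target. These are illustrations: the documents do not show that load shifted, by how much, or which way. With no shift there is no bias, only some avoidable noise if load affects readiness. The contemporaneous comparison is protected to the extent that its controls share the PACU and its load, which the plan leaves unstated. This is a worthwhile low-cost improvement to one of two primary comparisons; it does not invalidate the design or the power statement.

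**What to change.** 1. Add to X_i in the ITS model the number of patients in the non-study bays of the PACU at the patient's arrival, excluding the patient in question. Derive it in the same way from EHR arrival and departure times for study and control patients. Counting only non-study bays at arrival means that telemedicine in the study bays cannot directly change it.
2. Include the same variable in the contemporaneous propensity score, or as an adjustment in that comparison, and state which PACU the contemporaneous controls come from.
3. Report the census by phase, so readers can see whether load changed at the switch.

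The cost is one derived variable, a little programming and one degree of freedom; if census proves unrelated to readiness, almost no precision is lost. The main drawback is that census is an imperfect proxy: it does not capture staffing, so it may miss load per nurse or physician availability, and adjustment may remove only part of the bias.

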We will conduct focus groups with stakeholders to gain insights regarding their perceptions of barriers and facilitators related to the above-noted PACU functions before and after the implementation and use of a telemedicine center for the PACU. We will also gather perspectives from the stakeholders on the role and impact of the telemedicine center on their individual and team workflows in the PACU and between units during care transitions. Focus group participants will include nurses, anesthesiologists, surgeons, hospital administrators, and PACU telemedicine center clinicians. Our focus groups will be homogeneous in order to understand the clinician workflow based on their professional role, and their use of the telemedicine center in supporting their role and responsibilities. Each focus group will comprise five to six participants. This will allow in-depth discussions of the workflow problems and unintended

consequences caused by the implementation and use of the telemedicine center for the PACU. The focus group sessions will be guided by a semi-structured interview guide focused on the following themes: (1) PACU core functions, (2) PACU patient workflow, (3) PACU clinician activities and tasks, (4) tools and technologies used to support the PACU workflow, (5) major barriers to PACU functions, (6) use of a telemedicine intervention as a potential mechanism to support effective and efficient functioning of the PACU. We plan to conduct 6-8 focus group sessions (4 pre-intervention during observation phase, and 4 post-intervention during interaction phase) or until data saturation is attained.

Study Size

Patients are allocated to PACU bays according to the discretion of the nurse in charge of the PACU. Currently, approximately two patients per day are cared for in each bay in the participating PACU. Therefore, the telemedicine team will monitor approximately four patients per day over the course of the proof-of-concept study. We estimate that 500 patients will be included in this proof-of-concept study (250 per monitored phase) (Figure 4).

[figure not shown]

Figure 4. Allocation of sample size and PACU layout for proof-of-concept study

Statistical Methods

Primary Outcome

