Contemporaneous control patients will also be gathered. A propensity score for study inclusion will be generated as a function of (minimally) surgery performed, calendar time, time of day, age, and sex. 3:1 matched control patients will be included. Differences will be analyzed by t-tests using permutation calibration. Confidence intervals on the difference in mean time to discharge readiness will be generated by nonparametric bootstrap. We will include a sensitivity

analysis where the interrupted time series method includes historical and contemporaneous control patients with the treatment indicator T for study patients,

$$Y_i = f_1(t_i)I(t_i < t_0) + f_2(t_i)I(t_i \geq t_0) + X_i\beta + T_i + \epsilon.$$

Based on data from our EHR, patients are currently in PACU for a mean of 150 min (standard deviation = 65 min) before they are determined to be suitable for discharge. Based on these values, with 250 patients in each phase (observation and interaction), this observational before and after study will have >70% power with an alpha <0.005 and > 90% power with an alpha <0.05 to detect a mean decrease in 20 min (from 150 min to 130 min) to PACU discharge readiness time. Statistical testing will be with appropriate statistical software. Using non-parametric bootstrap of historical data and a 3:1 control sampling ratio, the average standard error on the difference in means under the null hypothesis was 5.5 minutes, giving an anticipated 95% confidence interval width of 22 minutes. A somewhat larger standard error will be encountered when adjusting for covariates or secular trends; however, this suggests that we will be able to resolve differences in PACU readiness times of 20-25 minutes. This difference of approximately a third a standard deviation is usually regarded as a “small-moderate” sized effect.

Secondary Outcomes

Hand-off quality assessment from the PACU nurse binary survey response will be analyzed using a logistic regression model adjusting for surgical service, age, and sex. Because observation resources are required for hand-off evaluations, no matching will be performed, and no contemporaneous controls will be gathered. Adjusted differences in rates of inadequate hand-off will be summarized with 95% confidence intervals and model-based p-values.

Observed reported hand-off communication quality will be presented as a purely descriptive result.

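### The main analysis against contemporaneous controls is an unadjusted t-test on the matched sample; eight factors the plan calls strongly prognostic enter only a sensitivity model

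*Combined protocol and SAP*

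**What the plan says.** All of this is in the combined protocol and SAP, mostly under Statistical Methods, Primary Outcome. That section opens its description of the analysis with "The primary outcome (time to PACU discharge readiness) will use two comparison groups".

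- **Historical controls.** These are propensity-matched 3:1 and analysed by interrupted time series. The model carries ten covariates, introduced as "Other patient factors known to strongly influence PACU length of stay" and ending with "history of postoperative nausea and vomiting, preoperative pain, and scheduled case duration) will be included as covariates". On matching, the plan adds: "No adjustment will be made for matching, but bootstrap methods will respect the matched" units.
- **Contemporaneous controls, matching.** "A propensity score for study inclusion will be generated as a function of (minimally) surgery performed, calendar time, time of day, age, and sex". The ratio is again 3:1.
- **Contemporaneous controls, analysis.** "Differences will be analyzed by t-tests using permutation calibration", with a nonparametric bootstrap interval for the difference in means. No covariate is named for either.
- **Contemporaneous controls, sensitivity.** The plan adds an "analysis where the interrupted time series method includes historical and contemporaneous control patients with the treatment indicator T for study patients". The covariate term appears in this model.

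The Study Size section says how patients reach the monitored bays: "Patients are allocated to PACU bays according to the discretion of the nurse in charge of the PACU".

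**The concern.** The plan names ten strong predictors of the outcome and adjusts for all of them in the main analysis of one comparison group. In the main analysis of the other group it adjusts for none and gives no reason. The unadjusted comparison is the one exposed to selection between bays at the same calendar time, since bay assignment is discretionary. The variables guaranteed to be in the matching score include no direct measure of acuity, such as ASA class, comorbidity count or sleep apnea.

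If study patients and matched controls still differ on such factors, the difference in means is biased, and so are its interval and test. Permutation calibrates the test to the hypothesis that study status is exchangeable. It cannot restore exchangeability that selection has broken. The adjusted result would exist, but only with sensitivity status and only in a pooled model.

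**Working it through.** **1. The plan's own figures.** These reproduce and are not in dispute. With SD 65 and 250 per phase, SE = 65 × √(2/250) = 5.81 min. For a 20 min difference, two-sided power is 93.1% at alpha 0.05 and 73.7% at alpha 0.005, against the stated >90% and >70%. The stated SE of 5.5 min with 3:1 sampling gives a 95% interval width of 2 × 1.96 × 5.5 = 21.6 min, stated as 22.

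**2. Covariate count.** The historical model has ten covariates. Age is also in the contemporaneous score, and specialty is largely implied by the procedure. That leaves 10 − 2 = 8: ASA class, comorbidity count, morbid obesity, sleep apnea, type of anesthesia, past PONV, pain before surgery and planned case length. Counted literally, with only age shared, it would be nine. The sensitivity model does not redefine its covariate vector; I take it to be the same ten.

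**3. Effect of residual imbalance on the error rate.** The documents give no covariate effects and no imbalances, so these inputs are assumptions:

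- bias = (difference in prevalence) × (effect of the factor in minutes)
- false-positive rate = P(|Z + bias/5.5| > 1.96)
- standardized difference for prevalence 30% in controls against p in study patients = (p − 0.30)/√{[0.30 × 0.70 + p(1 − p)]/2}

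| Assumed imbalance | Assumed effect | Bias | Bias/SE | Standardized difference | False-positive rate | Interval coverage |
|---|---|---|---|---|---|---|
| 5 points | 20 min | 1 min | 0.18 | 0.107 | 5.4% | 94.6% |
| 10 points | 30 min | 3 min | 0.55 | 0.211 | 8.5% | 91.5% |
| 15 points | 40 min | 6 min | 1.09 | 0.314 | 19.4% | 80.6% |

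Solving the other way, the rate reaches 7.5%, 10% and 15% at a bias of 2.55, 3.59 and 5.03 min.

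A second set of assumptions treats the eight factors jointly: bias = d × √R² × 65, where R² is the outcome variance they explain and d is the standardized imbalance in their combined effect. For R² of 0.05 to 0.3 and d of 0.1 to 0.3, bias runs from 1.5 to 10.7 min and the error rate from about 6% to 49%. Nothing in the documents favours the upper end of either range.

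**4. Whether permutation within matched sets helps.** I simulated 250 sets of one study patient and three controls, with one binary covariate (30% in controls) and no true effect. The total SD was set to 75.3 so that 75.3 × √(1/250 + 1/750) = 5.5; SD 65 would give 4.75. There were 2000 runs with 499 permutations each. Rejection at 5%:

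| Scenario | Pooled t-test | Within-set permutation | Regression on status + covariate | Mean unadjusted estimate | Mean adjusted estimate |
|---|---|---|---|---|---|
| No imbalance | 4.6% | 4.6% | 4.4% | −0.1 min | −0.1 min |
| 1 min bias | 5.7% | 5.8% | 4.8% | 0.9 min | 0.0 min |
| 3 min bias | 8.9% | 8.8% | 5.7% | 3.1 min | 0.1 min |
| 6 min bias | 19.9% | 19.3% | 5.5% | 6.1 min | 0.2 min |

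Monte Carlo error is about 0.5 points near 5% and 0.9 near 19%. Permutation leaves the bias in place; adjustment for the measured factor removes it.

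**The case against.** The strongest reply is that the plan already contains the adjusted analysis. Its one formal hypothesis is the discontinuity in the time-series model, which adjusts for all ten factors. The contemporaneous controls are an additional comparison. Propensity matching is itself control of confounding, and comparing matched means with an adjusted model as a check is a legitimate order. The score's list is a stated minimum, so more factors can be added. The exact procedure probably carries much of planned case length and anesthesia type, so the factors with no proxy may be nearer six than eight. A factor that predicts the outcome confounds only if it also relates to bay assignment, and the documents do not say that these do.

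The numerical case can also be pressed. Every bias is assumed. The simulation adjusts for the very confounder it built in, so recovering the null is a known property and not evidence about this study. The plan does not tie the 5.5 min SE specifically to this comparison, and does not say whether contemporaneous controls cover one phase or both. Even 6 min is only 30% of the 20 min target effect (6/20).

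Much of this stands. The size is unknown, the proxy argument is fair, and the limitations section already declines causal attribution for the before-and-after design. Two parts do not answer the point. Permission to extend the score is not a commitment to do so. And the pooled time-series model combines both control groups, so it is not an adjusted version of the matched contemporaneous contrast.

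**Conclusion.** The concern holds. One of the two primary comparisons has an unadjusted main estimate, although the plan itself names eight further strong predictors and already needs them for these controls. The numerical effect cannot be known from the documents: it is negligible if matching balances these factors well, and the error rate passes 10% once residual bias exceeds about 3.6 min at an SE of 5.5 min. Those figures assume that this SE applies to the contemporaneous comparison, and the simulation assumes 250 study patients in it.

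The change should be made, but it is not critical. The stated hypothesis rests on the adjusted model, and no stated power, sample size or SE figure is affected.

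**What to change.** In Statistical Methods, Primary Outcome, for contemporaneous controls:

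1. Make the main estimate a regression of time to readiness on study-patient status plus the ten covariates of the historical model, fitted in the matched sample. Keep the t-test as a sensitivity analysis.
2. State that permutation is of study status within matched sets, and that the matched-unit bootstrap rule given for historical controls applies here too. The bootstrap rule can reasonably be read to carry over; the permutation unit is not stated.
3. Report standardized differences on the ten covariates after matching.

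Adding the eight factors to the propensity score is optional.

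The cost is a few sentences and a few lines of code. No new data are needed: the planned sensitivity model already requires these covariates for contemporaneous controls, and the Data Collection section takes patient characteristics from the EHR. The drawbacks are a little more analysis work, and harder matching if the score is lengthened. Adjustment will not remove selection by the charge nurse on factors outside the list.
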